5.1.1.2. Vital Signs, Height and Weight

Vital signs – including pulse rate, respiratory rate, systolic and diastolic blood pressure, and body temperature – will be obtained at the time points specified in the schedule of assessments (Appendix B of study protocol). On dosing days, vital signs will be recorded pre-infusion, every 30 minutes (± 10 min) during the infusion and every 30 minutes (± 10 min) from 0 to 2 hours after the end of the infusion.

Body weight and height will be measured, prior to SBC-102 infusion at study at the time points specified in the schedule of assessments (Appendix B of the study protocol). Height is measured in inches or centimeters, and weight is recorded in pounds or kilograms. Both will be reported in metric units.

5.1.1.3. Physical Examination

A complete, age-appropriate physical examination will be performed by the Investigator or qualified designee, at the time points specified in the schedule of assessments. The examination will include an assessment of the subject's general appearance, skin, head (including head circumference for children up to 3 years of age), eyes, ears, nose, throat, heart, lungs, abdomen, extremities/joints, and neurological status. Abnormal findings will be recorded in the electronic Case Report Form (eCRF).

Every physical examination will also include the following:

- Child-Pugh Score (see Appendix A of Study Protocol);
- Abdominal photograph for subjects < 4 years of age at Screening;
- Liver size: A clinical assessment of liver size (palpable/non palpable and centimeters below costal margin), regularity (smooth/nodular), and sensitivity (tender/nontender);
- Spleen size: A clinical assessment of spleen size (palpable/nonpalpable and centimeters below costal margin), regularity (smooth/nodular), and sensitivity (tender/nontender);
- Lymphadenopathy: An assessment of the size, location, and character of any palpable lymph nodes. Areas to be examined include cephalic (occipital, preauricular, postauricular, submental, submandibular), cervical, clavicular, axillary, and inguinal. Any enlarged nodes will be characterized as tender or nontender;

- Arterial disease: A clinical assessment of the right and left posterior tibialis and dorsalis pedis pulses and carotid bruits;
- Skin manifestations: A clinical assessment of signs of liver disease and portosystemic anastomoses such as
 periumbilical venous engorgement (caput medusae), spider nevia, or gynecomastia, dyslipidemia such as
 xanthomas (tendinous, tuberous) and xanthelasma, and allergies including assessment of allergic skin
 rashes.

5.1.1.4. Laboratory Assessments

Blood and urine samples for clinical laboratory tests will be collected at the time points indicated in the schedule of assessments. Table 2 lists the laboratory panels and associated tests to be performed on blood (or urine) samples. Note that not all tests are performed at the same time points due to limitations on blood volume collection that is considered acceptable in young children with very small total circulating blood volumes (see Section 5.9 of study protocol for further details).

A central laboratory will be responsible for analysis of all laboratory tests, with the exception of prothrombin time (international normalized ratio) [PT(INR)], activated partial thromboplastin time (aPTT), urinalysis, and urine pregnancy.

Clinically significant changes from a subject's baseline value or previous values will be recorded as AEs.

Table 2:Clinical Laboratory Tests

Laboratory Panel	Tests
Hematology	White blood cell count; red blood cell count; hemoglobin; hematocrit; mean corpuscular volume, hemoglobin, and hemoglobin concentration (MCV, MCH, MCHC); platelet count; neutrophil; lymphocytes; monocytes; eosinophils; basophils; peripheral smear for examination of cell morphology
Liver Function Tests	ALT, AST, alkaline phosphatase, GGT, albumin, bilirubin (direct, indirect, total)
Serum Lipids	LDL-C, total cholesterol non-HDL-C, triglyceride, HDL-C
Other Chemistries	Serum electrolytes (sodium, potassium, chloride, calcium, magnesium, phosphorus), glucose, creatinine, bicarbonate, total protein, blood urea nitrogen, high-sensitivity C-reactive protein HbA1c
Macrophage Activation Markers	serum chitotriosidase, serum ferritin, hs-CRP , CK-18
Urinalysis ¹	pH, clarity, color, specific gravity, glucose, ketones, blood, protein, nitrite, and leukocytes (microscopic examination will only be done if urinalysis is positive for blood, nitrite, or leukocytes, or if protein is >1+)
Viral Hepatitis Screen	HBsAq and HCV serology
Alcohol Use	CDT
Coagulation Parameters ¹	PT (INR), aPTT
Pregnancy ²	Serum hCG at Screening and urine hCG1 at all other visits
Anti-drug Antibody	Anti-sebelipase alfa antibody
Exploratory Biomarkers	See Section 5.9.5 of Study Protocol
LAL Enzyme Activity	Dried blood spot. See Section 5.9.6 of Study Protocol
DNA Sample	See Section 5.9.7 of Study Protocol
PK Samples	See Section 5.9.4 of Study Protocol
Malnutrition Markers and Fat Soluble Vitamins	See Laboratory Manual for details
Test performed by a local laboratory. Performed for female subjects of childbearing potential only.	•

5.1.1.5. Concomitant Medications and Treatments

Prior medications are defined as medications taken or treatments received by subjects prior to the first dose of SBC-102. Concomitant medications are defined as medications taken or treatments received by subjects during the study after first dose of SBC-102.

Concomitant medications include prescription and over-the-counter medications, herbal medications, prophylactic and therapeutic vaccines, vitamins, and dietary supplements. Concomitant treatments include diagnostic, palliative, or interventional procedures (e.g., lipid-lowering diet, surgery, physical therapy). Information on all concomitant medications and treatments will be recorded in the eCRF and will include the name of the medication (brand or generic) or therapy, reason for use, start date, stop date, dose, route of administration (if applicable), and frequency of administration.

5.1.1.6. Electrocardiogram (ECG)

Age-appropriate 12-lead ECG measurements will be obtained at the time points specified in the schedule of assessments. ECGs will be reviewed by a qualified clinician, and any abnormalities will be specified as CS or NCS.

5.1.1.7. Anti-drug Antibodies (ADAs)

Blood samples will be collected to test for antibodies to SBC-102 in plasma just prior to dosing, at Baseline and every 4 weeks until Week 12. After Week 12, ADA samples will be collected every 12 weeks and at end of study (or early withdrawal) visit, as well as after an IAR.

5.1.1.8. Denver II Developmental Screening Test (DDST)

The Denver II Developmental Screening Test (DDST) will be administered at the time points specified in the schedule of assessments.

The test is a standardized measure to assess development in children from 1 month to 6 years of age (Frankenberg et al., 1992). It includes performance-based and parent-reported items in 4 functional areas: fine motor-adaptive, gross motor, personal-social, and language skills. The test was normed on a diverse sample of children who were full term and had no obvious developmental disabilities; the norms indicate when 25%, 50%, 75%, and 90% of children passed each item. The instrument has good inter-rater and test-retest reliability (correlations \geq 0.90 for most tests).

The test must be administered by a trained clinician and takes an average of 10 to 20 minutes to complete, and up to an hour depending on the age of the child and number of assessments completed. Administration and scoring of DDST is based upon the child's age.

Refer to the Study Operations Manual (SOM) for further information on administration and scoring of DDST.

5.2. Efficacy

5.2.1. Secondary Endpoint(s)

Efficacy endpoints will include absolute changes or percent changes over time from Baseline as follows: Decrease in Alanine Aminotransferase (ALT); Decrease in Aspartate Aminotransferase (AST); Decrease in Low Density Lipoprotein Cholesterol (LDL-C); Increase in High Density Lipoprotein Cholesterol (HDL-C); Decrease in non-HDL-C; Decrease in triglyceride; Decrease in Child-Pugh status for subjects with Child-Pugh class C or B at Baseline; Decrease in United Kingdom Model for End-Stage Liver Disease (UK-MELD) score; Improvement in liver histopathology; Decrease in liver and spleen volume by magnetic resonance imaging (MRI); Decrease in liver fat fraction by MRI.

Other efficacy endpoints will be determined as follows:

- For Subjects ≤24 months of age, z-scores and percentile scores based on World Health Organization (WHO) growth charts (WHO Multicentre Growth Reference Study Group, 2006 and 2007) will be determined for the following parameters:
 - Weight-for-age (WFA);
 - Weight-for-length;
 - Length-for-age;
 - o Body Mass Index (BMI)-for-age;
 - o Head circumference-for-age.
- For subjects >24 months of age to 18 years, z-scores and percentile scores based on Centers for Disease Control and Prevention (CDC) growth charts (Kuczmarski et al., 2000) will be determined for the following parameters:
 - o WFA;
 - Weight-for-stature (weight-for-height);
 - Stature-for-age (SFA);
 - o BMI-for-age.
- For all subjects <18 years, the proportion of subjects who meet criteria for under nutrition (underweight, wasting, and stunting) based on WFA, weight-for-length/weight-for-stature, and length-for-age/SFA, respectively (UNICEF, 2009), and combinations of these indicators, will be determined.
- Additional clinical, biochemical and hematological abnormalities including: total and conjugated bilirubin;
 Gamma glutamyltransferase (GGT); hemoglobin level; platelet count; and markers of macrophage activation, including absolute reductions in serum ferritin, serum chitotriosidase and high-sensitivity C-reactive protein (hs-CRP).
- Changes from baseline in scores from different HRQOL instruments briefly described in Section 5.2.1.3 below.

5.2.1.1. ALT, AST, LDL-C, non HDL-C, Triglycerides and HDL-C

Blood samples to determine ALT, AST, non HDL-C, triglycerides and HDL-C are collected as part of clinical laboratory assessments, as specified in Table 2, and at timepoints specified in the schedule of assessments.

5.2.1.2. Child-Pugh Score

See Appendix A of the study protocol.

5.2.1.3. Health-Related Quality of Life (HRQOL)

HRQOL questionnaires will be completed at the time points specified in the schedule of assessments for subjects who are \geq 5 years of age. The specific HRQOL questionnaires completed by each subject will be based on the respondent's age on the date that informed consent is obtained as indicated in Table 3. The questionnaires will be administered prior to any other study procedures being conducted at that visit.

The 13-item Functional Assessment of Chronic Illness Therapy (FACIT) Fatigue scale was developed to measure levels of fatigue in people living with a chronic disease. In this study, the FACIT-Fatigue scale version 4 will be self-administered by all subjects who are ≥17 years of age at informed consent.

The Chronic Liver Disease Questionnaire (CLDQ) is a disease-specific instrument designed to assess HRQOL in subjects with chronic liver disease (Younossi et al., 1999). The CLDQ will be self-administered by all subjects who are ≥17 years of age at informed consent.

The Pediatric Quality of Life Inventory TM (PedsQLTM) is composed of generic core scales and disease-specific modules. The 23-item PedsQLTM 4.0 Generic Core Scales was designed to measure the core dimensions of health, as delineated by the World Health Organization, as well as role (school) functioning in healthy children and those with acute or chronic health conditions. The PedsQLTM Generic Core Scales includes 4 multidimensional scales of physical functioning (8 items), emotional functioning (5 items), social functioning (5 items) and school functioning (5 items). In addition to the total scale score (all 23 items), two summary scores, the Physical Health Summary (8 items) and Psychosocial Health Summary (15 items), are also reported. In this study, the PedsQLTM 4.0 Generic Core Scales will be self-administered by subjects who are 5 to <18 years of age on the date of informed consent, using one of the three self-report forms (ages 5-7, 8-12, or 13-18), as appropriate to the subject's age (Varni et al., 2009). Parent proxy reports will not be used in this study.

Sample questionnaires and detailed instructions on administration of HRQOL questionnaires are provided in the SOM. Also see Section 9.4.9 for details on derivation of summary scores from the HRQOL instruments.

 Patient Age
 FACIT-Fatigue
 CLDQ
 PedsQL™ Generic Core Scales

 5 to <17 years¹	X
 X

 17 to 18 years¹
 X
 X

 >18 years¹
 X
 X

Table 3: Health-Related Quality of Life Assessments

5.3. Pharmacokinetic Endpoints

Blood samples for determination of SBC-102 serum concentrations will be collected from subjects <18 years of age, from subjects with severely impaired liver functioning (e.g. based on imaging, biopsy or Child-Pugh Class C status at Screening), and for subjects who have previously undergone liver or hematopoietic stem-cell transplantation. Sampling will be completed - as blood volume permits - at Baseline, Week 24 and Week 48, and on the day of a dose increase, as applicable. Details on sampling time and sampling strategy are described in the study protocol (Section 5.9.8).

PK parameter estimates to be reported may include: serum clearance and apparent volume of distribution; Area Under the Concentration Curve (AUC), maximum observed concentration (Cmax), time to maximum observed concentration (Tmax), and terminal elimination half-life (t1/2). Details of pharmacokinetic analyses will be described in a separate analysis plan.

Further details will be provided in a separate analysis plan.

5.4. Exploratory Biomarker Assessment

Blood samples (for serum isolation) will be obtained at the time points specified in the schedule of assessments, where local regulations and blood volume limitations permit, for exploratory analyses to identify and evaluate disease-related biomarkers. The intent is to investigate baseline disease and dynamic markers that will enable the Sponsor to better understand the pathogenesis of LAL-D and related comorbidities and response to SBC-102 therapy. Given the rarity of LAL-D and the paucity of information on disease characteristics, the definitive list of analytes remains to be determined.

No biomarkers are planned for analysis at this time.

Based on the patient's age on the date that informed consent is obtained.

6. DATA SETS ANALYZED (STUDY POPULATIONS)

Safety will be examined for the Full Analysis Set overall and, as sample size permits, adverse events will besummarized by age. Efficacy will be examined for the Full Analysis Set and, as sample size permits, summarized by age, gender, baseline use of lipid-lowering medication, genetic mutation category, baseline fibrosis or cirrhosis status, baseline ALT (>1.5 x ULN and <=1.5 x ULN), and other potential subgroups of interest at the time of analysis. Summaries of HRQOL may be summarized by subgroups.

6.1. Full Analysis Set (FAS)

This analysis set will include all subjects who received at least 1 infusion of SBC-102. This analysis set will be used for analysis of safety, efficacy, and subject health outcomes data.

7. STATISTICAL ANALYSIS

Alexion or designee will be responsible for data collection, reviewing and validating all the information in the eCRFs, statistical analysis, and generation of the clinical report. The final statistical analysis will not begin until the entire database is locked and signed off.

The Alexion Biostatistics Department or designee will perform the statistical analysis of the data derived from this trial. The analysis will be performed using the SAS® statistical software system Version 9.2 or higher.

No formal inferential statistical testing will be performed. As appropriate, 95% two-sided confidence intervals (CIs) will be calculated around the estimates based on the exact binomial distribution (Clopper-Pearson method) for binomial endpoints and the t-distribution for continuous endpoints. P-values and 95% confidence intervals, where presented, will be considered descriptive and will be provided to facilitate clinical review and interpretation.

All data collected in this study will be provided in subject data listings sorted by subject number; the dose of SBC-102 temporally associated with the data will be included on the listing. Summary tables and/or graphs will be presented for each endpoint, as appropriate to the data, by evaluation time point. Visits will be summarized as collected, and data collected from unscheduled visits will be included in subject listings. Unless otherwise noted, the following standard conventions will be used for creating descriptive summaries:

- Continuous numeric endpoints will be summarized by providing the number of subjects with nonmissing data, the mean and standard deviation (SD) of the data, and the minimum, first quartile (Q1), median, third quartile (Q3), and maximum value;
- For categorical endpoints, the number and percentage of subjects with each possible outcome will be displayed. The denominator for percentages will not include subjects with missing data;
- Mean, median values, Q1 and Q3 will be presented with one decimal point more than the original value, SD will be displayed with two decimal points more than the original value and minimum/maximum values will have the same number of decimal points as the original value;
- In frequency tables the percentage will be displayed with no decimal place.

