5.9.3. Clinical Laboratory Collection and Analysis

Laboratory samples will be collected under the following conditions:

- Blood samples will be drawn prior to the study drug infusion on infusion visits, and in the morning (whenever feasible) on noninfusion visits;
- Subjects ≥ 18 will fast for at least 9 hours prior to collection of blood samples;
- Subjects will refrain from ingestion of alcohol for 24 hours prior to collection of blood samples for lipid and liver panels.

Refer to the SOM and Laboratory Manual for further details regarding the collection, processing, and storage of clinical laboratory samples.

A central laboratory will be responsible for analysis of all laboratory tests, with the exception of prothrombin time (international normalized ratio), activated partial thromboplastin time, urinalysis, and urine pregnancy.

Any identified laboratory abnormalities will be specified as CS or NCS by the Investigator or designee. In the event of unexplained clinically significant abnormal laboratory test results, the tests will be repeated as soon as possible (preferably within 24 hours of receiving the result) and followed up until they have returned to within the normal range and/or an adequate explanation has been identified. Clinically significant changes from a subject's baseline value or previous values will be recorded as AEs.

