5.9.4. Clinical Laboratory Collection for Dose Changes

Subjects who undergo a dose modification, as described in [Section 6.1](#), or changes in lipid-lowering therapies, as described in [Section 4.5](#), will have the following additional laboratory monitoring schedule of selected analytes:

- Prior to the first infusion of new dose/schedule or change in lipid-lowering medication: serum lipid panel, liver panel, hematology, serum chemistry, ferritin, hs-CRP;
 - For dose modifications only: at the first infusion of new dose/schedule, a predose blood sample will be collected for ADA and serial blood samples will be collected for a determination of sebelipase alfa serum concentrations according to the sampling schedule shown in [Table 2](#) (pediatric subjects) or [Table 3](#) (adult subjects).
- 4 weeks after starting new dose/schedule or change in lipid-lowering medication: serum lipid panel, liver panel;
- 8 weeks after starting new dose/schedule or change in lipid-lowering medication: serum lipid panel, liver panel;
- 12 weeks after starting new dose/schedule or change in lipid-lowering medication: serum lipid panel, liver panel, hematology, serum chemistry.

In the event that any of the above additional laboratory monitoring time points coincides with the standard laboratory assessment, the standard laboratory assessment will supersede the additional laboratory monitoring (see [Appendix B](#)).

If a subject's blood volume threshold for weight or clinical status limit collection of samples on the scheduled visit date, the Sponsor or medical monitor should be consulted for guidance with regard to a modified schedule for that visit.

Table 1 Clinical Laboratory Tests

| Laboratory Panel | Tests |
|---|---|
| Hematology | White blood cell count; red blood cell count; hemoglobin; hematocrit; mean corpuscular volume, hemoglobin, and hemoglobin concentration (MCV, MCH, MCHC); platelet count; neutrophil; lymphocytes; monocytes; eosinophils; basophils; peripheral smear for examination of cell morphology |
| Liver Function Tests | ALT, AST, alkaline phosphatase, GGT, albumin, bilirubin (direct, indirect, total) |
| Serum Lipids | LDL-C, total cholesterol non-HDL-C, triglyceride, HDL-C |
| Other Chemistries | Serum electrolytes (sodium, potassium, chloride, calcium, magnesium, phosphorus), glucose, creatinine, bicarbonate, total protein, blood urea nitrogen, hs-CRP |
| | HbA1c |

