6.1.2. Accelerated Dose Escalation Criteria

Dose escalation may be accelerated in exceptional cases with a particularly severe clinical presentation or evidence of rapid or substantial clinical deterioration, including but not limited to inadequate weight gain, ongoing weight loss deemed to be related to LAL Deficiency or a symptomatic progression of liver disease. Dose escalation will occur at the discretion of the Investigator and with approval of the Sponsor. A $3 \text{ mg}\cdot\text{kg}^{-1}$ qow dose may be considered after at least 4 consecutive infusions at the initial $1 \text{ mg}\cdot\text{kg}^{-1}$ qow dose. A further increase in dose to $3 \text{ mg}\cdot\text{kg}^{-1}$ qw may be considered if a subject continues to demonstrate significant clinical progression after receiving at least 4 consecutive infusions at the $3 \text{ mg}\cdot\text{kg}^{-1}$ qow dose.

In special cases, and only with approval from the Sponsor, it may be allowable to increase the dose to $3 \text{ mg}\cdot\text{kg}^{-1}$ qw, without mandating 4 infusions of qow dosing.

[figure not shown]
Significant clinical progression of liver disease is met if the subject presents with the following criteria:

- Confirmed elevation of ALT or AST to $> 5 \times$ upper limit of normal and at least twice the highest pre-treatment value and presence of one of the following:
 - Increase of total bilirubin to $> 3 \times$ upper limit of normal and at least twice the highest pre-treatment value;
 - Prolongation of prothrombin time (international normalized ratio) ≥ 4 seconds above Baseline;
 - Development or worsening of ascites;
 - Development of encephalopathy.

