7.2.3. Laboratory Tests

Observed measurements and changes from Baseline to each study time point in clinical laboratory data will be summarized. Frequencies of results relative to the laboratory normal range as well as shift tables showing the change from baseline to post-baseline relative to the normal range will be summarized, if sufficient data are available for analysis. Summaries will be presented for liver function tests, serum lipids, hematology, serum chemistry, HbA1c, and coagulation parameters as identified in Table 2, Clinical Laboratory Tests, above.

Plots of mean observed values, absolute change from baseline and mean percent change from baseline over time with standard error bars may be prepared for the following:

- Liver function tests: ALT/AST, GGT, total bilirubin, direct bilirubin, indirect bilirubin, albumin, alkaline phosphatase
- Lipids: total cholesterol, LDL-C, non-HDL-C, HDL-C, triglycerides
- Hematology: hemoglobin, platelets

Also see Section 7.3.2 Clinical Laboratory Tests as described in the Efficacy Analyses section.

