7.3.2. Clinical Laboratory Tests

Both the change and the percent change from Baseline in serum liver biochemical parameters (liver function tests), serum lipids, hemoglobin levels, and platelet count will be tabulated for each evaluation timepoint. Data will be summarized for the endpoints as continuous variables. In addition, summaries of categories relative to the upper limit of normal ($\le 1 \text{ x ULN}$, 1 to $\le 1.2 \text{ x ULN}$, 1.2 to $\le 1.5 \text{ x ULN}$, 1.5 to $\le 2 \text{ x ULN}$, >2 x ULN) will be provided with shifts from baseline to post-baseline in these categories. Waterfall plots showing the percent change from baseline to Week 96 will be presented.

- Liver function tests: ALT/AST, GGT, total bilirubin, direct bilirubin, indirect bilirubin, albumin, alkaline phosphatase
- Lipids: total cholesterol, LDL-C, non-HDL-C, HDL-C, triglycerides
- Hematology: hemoglobin, platelets

The UK-MELD assessment, which is computed from clinical laboratory values, will be summarized similarly to laboratory data, although these scores will not be compared against standard laboratory reference ranges for individual laboratory assessments.

Also see Section 7.2.3, Laboratory Tests, as described in the Safety Analysis section.

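### The laboratory category and shift tables cannot show worsening above 2× ULN and may omit off-schedule peaks, and the SAP does not say how the dose-change panels are tabulated

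*SAP*

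**What the plan says.** SAP section 7 sets the general rule: "Summary tables and/or graphs will be presented for each endpoint, as appropriate to the data, by evaluation time point". It continues: "Visits will be summarized as collected, and data collected from unscheduled visits will be included in subject listings". Continuous endpoints are described at each time point with the mean and SD and with "the minimum, first quartile (Q1), median, third quartile (Q3), and maximum value". The SAP has no worst-value or any-time laboratory summary.

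For safety, SAP 7.2.3 provides that "shift tables showing the change from baseline to post-baseline relative to the normal range will be summarized", if there are enough data. SAP 7.3.2, under efficacy, adds "summaries of categories relative to the upper limit of normal" with shifts between them. There are five bands, and the highest is everything above 2× ULN.

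Three protocol sections bear on this:
- Section 5.9.4: subjects with a dose or lipid-drug change "will have the following additional laboratory monitoring schedule of selected analytes". It includes liver and lipid panels before the change and 4, 8 and 12 weeks after it.
- Section 5.9.3: unexplained, clinically significant abnormal results are repeated promptly.
- Section 6.1.2: significant progression of liver disease requires a confirmed ALT or AST above 5× ULN "and at least twice the highest pre-treatment value and presence of one of the following": total bilirubin above 3× ULN and at least doubled, prolonged prothrombin time, ascites, or encephalopathy.

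**The concern.** Safety is the primary objective, and liver and lipid values are what the protocol watches most closely around dose changes. Two of the three routine escalation criteria in protocol 6.1.1 are transaminases, or LDL-C or triglycerides, that remain abnormal. A subject escalated on one of these is already outside the normal range for that analyte, so a normal-range shift table cannot show that it worsened further. The ULN bands help only up to 2× ULN.

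A by-visit table also depends on which draws carry a visit label. If a peak appears only at a symptom-directed visit or a prompt repeat, the natural reading of SAP section 7 puts it in a listing. If the dose-change panels have no tabulation rule, the response to a higher dose may be spread over visit rows that mix subjects at different times since their change, or may appear in no row.

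**Working it through.** The plan states no figure for this point. Two direct checks apply.

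**1. What the category tables can show.** Inputs: the SAP 7.3.2 bands (≤1, 1 to 1.2, 1.2 to 1.5, 1.5 to 2, >2× ULN), the SAP 7.2.3 normal-range shift, and the ALT/AST condition of protocol 6.1.2 (later value >5× ULN and ≥2 × highest pre-treatment value). For illustration, the baseline is taken as the highest pre-treatment value.

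| Baseline → later (× ULN) | 7.2.3 shift | 7.3.2 shift | ALT/AST condition |
|---|---|---|---|
| 1.6 → 5.1 | none (high to high) | yes, into >2 | met: 5.1 ≥ 2 × 1.6 = 3.2 |
| 1.6 → 12 | none | yes, into >2 | met |
| 2.5 → 5.1 | none | none | met: 5.1 ≥ 2 × 2.5 = 5.0 |
| 4 → 8 | none | none | met: 8 ≥ 2 × 4 = 8 |
| 3 → 5.1 | none | none | not met: 5.1 < 2 × 3 = 6 |

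From a baseline of 2× ULN or less, a rise above 5× appears as a shift, but its size is lost. From a baseline above 2×, it does not appear at all. Bilirubin behaves the same way: 2.1× to 4.2× ULN is above 3× and doubled (2 × 2.1 = 4.2), yet stays in the top band.

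**2. Where the dose-change panels fall.** Inputs: standard liver and lipid panels at Weeks 0, 2, 4, 8 and 12, then every 12 weeks to Week 144 (protocol Appendix B); dose-change panels at w+4, w+8 and w+12 for a change at Week w (protocol 5.9.4).

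- For w after Week 12, a draw meets a standard panel only at a multiple of 12. The three draws are 4 weeks apart, so at most one can be at, or within 7 days of, a multiple of 12.
- If w is divisible by 4, exactly one coincides. Example: w = 16 gives Weeks 20, 24 and 28, and only 24 is standard.
- If w is even but not divisible by 4, none does, and the nearest panel is at least 2 weeks away. Example: w = 18 gives Weeks 22, 26 and 30.

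Routine escalation needs 8 every-other-week infusions (Weeks 0 to 14), so the earliest is Week 16. Even weeks from 16 to 84 keep the last draw within Week 96:

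- Possible change weeks: (84 − 16)/2 + 1 = 35, giving 35 × 3 = 105 draws.
- Weeks divisible by 4: (84 − 16)/4 + 1 = 18, so 18 of 105 draws (17%) are on a standard panel.
- Change weeks with none: 35 − 18 = 17.
- Draws on a named visit column (every 4 weeks): 18 × 3 = 54 of 105.

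Starting at Week 8, the earliest accelerated escalation after 4 infusions, gives 20 of 117 draws (17%), no coincidence for 19 of 39 change weeks, and 60 of 117 draws on a named visit column.

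**The case against.** The strongest reply is that the risk is covered elsewhere. SAP 7.3.2 tabulates change and percent change at every time point, and the summaries include the maximum. A scheduled-visit rise from 2.5× to 5.1× ULN is (5.1 − 2.5)/2.5 = 104% and would enter that summary. Clinically significant laboratory changes are recorded as adverse events whatever the visit type. SAP 7.3 allows dose-specific baselines, listings carry the dose, and a Safety Committee reviews aggregated safety data about every 6 months. With about 20 (SAP 9.3) to 30 (protocol 8.2) subjects, listings can be read by hand.

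Much of this stands, and it means that a large scheduled-visit rise is unlikely to vanish. But the maximum covers only tabulated draws and is not expressed in multiples of ULN. The waterfall plots show Week 96 only. Adverse-event recording rests on Investigator judgement, and SAP 4.2 drops the clinical-significance flag for laboratory results. Dose-specific baselines apply as appropriate, under efficacy. A percent change of 100% is also not the 6.1.2 doubling rule, because the SAP baseline averages up to three values while 6.1.2 uses the highest pre-treatment one.

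The repeat draws matter less than they first appear to. A repeat follows an abnormal result that, if taken at a scheduled visit, is already tabulated. What may be missing is a higher repeat value or the confirmation that 6.1.2 asks for.

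It is also fair that 6.1.2 is a dose-escalation rule, and that no document promises a safety count of it.

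**Conclusion.** The point holds in a limited form. The category and shift tables cannot show worsening in a subject already above 2× ULN, cannot identify the 6.1.2 levels, and may omit peaks seen only off schedule. The tabulation of the dose-change panels is unspecified.

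A reader might infer that the post-escalation panels are excluded from the tables as unscheduled visits. The documents do not support that. Protocol section 5 describes unscheduled visits as discretionary and symptom directed, whereas the panels in 5.9.4 are set by the protocol. About half of the possible draws fall on a named visit week and could be tabulated there. Even for true unscheduled visits, the SAP says that the data go into listings; that they go nowhere else is an inference.

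Nor do the documents report lipid rises after a later escalation. The LAL-CL01 rises followed the start of treatment, a period that the Week 2 to 12 panels cover here. The effects on serum lipids appeared more pronounced at 3 mg/kg, which is a reason to look after escalation but not evidence of a missed signal.

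The size in subjects is unknown. The 17% is a share of possible calendar weeks. The number of dose changes is not given, nor is the number of subjects above 2× ULN at baseline. Elevated ALT is only one optional entry criterion, for those under 4 years, and is not a listed criterion for older subjects.

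**What to change.** Amend SAP 7.2.3 and 7.3.2, using data already collected:

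1. Add abnormality and shift tables on the worst post-baseline value from any source (scheduled, dose-change, repeat, unscheduled). State the adverse direction for each analyte, label the tables clearly, and show them beside the by-visit tables.
2. For ALT, AST and total bilirubin, split the top band at the protocol's own levels: >2 to 3×, >3 to 5× and >5× ULN. Count subjects who at any time met the laboratory part of protocol 6.1.2, including at least twice the highest pre-treatment value.
3. For subjects with a dose change, tabulate liver and lipid change from the pre-change sample at 4, 8 and 12 weeks, and state how these draws enter the by-visit tables.

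The cost is SAP wording and a few extra tables. The downside is that worst-value rates will be higher than by-visit rates, which is why both should be shown. The extra bands stop at ALT, AST and total bilirubin because the documents give no 3× or 5× level for other analytes. No change to any clinical threshold or dosing rule is proposed.
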